3. PATIENT SELECTION

3.1. Inclusion Criteria

- A. Signed Informed Consent
- B. Ability to comply with the protocol
- C. Age \geq 18 years
- D. Histologically or cytologically documented, locally advanced or metastatic (i.e., Stage IIIB not eligible for definitive chemoradiotherapy, Stage IV, or recurrent) NSCLC (per the American Joint Committee /AJCC staging system)

- E. ECOG performance status of 0 to 2
- F. Measurable disease, as defined by RECIST v1.1. Previously irradiated lesions can be counted as target lesions if clearly progressing after radiation.
- G. Chemotherapy-naive and treated patients will be eligible, with no limit on number of prior therapies. Patients with NSCLC known to harbor an ALK rearrangement, or EGFR mutation known to be sensitive to FDA-approved tyrosine kinase inhibitors (TKI), are only eligible after experiencing disease progression (during or after treatment) or intolerance to an FDA approved EGFR TKI or ALK TKI, respectively.
 - a. Patients with TKI-treated EGFR mutant NSCLC harboring the secondary EGFR T790M tumor must have received prior osimertinib
 - b. Patients with crizotinib-treated ALK rearranged NSCLC must have received a next generation ALK inhibitor (e.g. ceritinib, alectinib or brigatinib)
- H. Prior palliative radiotherapy must have been completed at least 2 weeks before the first dose of study drug.
- I. Anti- PD-1 Axis therapy (anti-PD-1 or anti-PD-L1, e.g. nivolumab, pembrolizumab, atezolizumab, durvalumab, avelumab) must be the most recent systemic anti-tumor treatment received in all patients, with documented progressive disease. Last administration of anti-PD-1 axis therapy must have been at least 3 weeks before the first dose of study drug.
 - a. Patients to be enrolled to the primary cohort (primary resistance) must have had progressive disease or stable disease less than 24 weeks as the best clinical response to anti-PD-1-axis monotherapy
 - b. Patients to be enrolled to the exploratory cohort (acquired resistance) must have had stable disease for at least 24 weeks, partial response, or complete response as the best clinical response to anti-PD-1-axis monotherapy, with subsequent progression of disease
- J. At least one tumor amenable to incisional, excisional, core or forceps (transbronchial) biopsy. Patients must be willing to undergo tumor biopsies before starting trial therapy, and 9 to 10 weeks after initiation of therapy.

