- I. Subjects must not have received vaccines containing live virus for prevention of infectious diseases within 12 weeks prior to the first dose of study drug.
- a. The use of inactivated seasonal influenza vaccines (eg, Fluzone®) will be permitted on study without restriction.
- J. Any approved systemic anti-cancer therapy, within 3 weeks prior to initiation of study treatment; the following exception is allowed:
- TKIs approved for treatment of NSCLC discontinued > 7 days prior to Cycle 1, Day 1. The baseline scan must be obtained after discontinuation of prior TKIs.
- K. Treatment with any other investigational agent or participation in another clinical trial with therapeutic intent within 21 days prior to enrollment; the following exceptions are allowed:
- Unapproved/experimental TKIs discontinued 14 days prior to Cycle 1, Day 1
- L. Known infection with HIV, HBV or HCV. Patients with prior exposure to hepatitis, but no evidence of active or chronic infection, may be eligible.
- Subjects with positive hepatitis C antibody and negative quantitative hepatitis C by polymerase chain reaction are eligible.
- M. Active systemic infection requiring systemic antibiotic treatment within 72 hours prior to first dose of study treatment
- N. Uncontrolled intercurrent illness including, but not limited to, symptomatic congestive heart failure, unstable angina pectoris, or psychiatric illness/social situations that would limit compliance with study requirements
- O. Major surgery or traumatic injury within 4 weeks of starting study drug
- P. Women who are pregnant or lactating.

- Q. Any underlying medical condition that in the Principal Investigator's opinion will make the administration of study drug hazardous to the patient or would obscure the interpretation of adverse events.

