5.1. Screening Period

The following procedures and tests will be completed during this period to determine eligibility. All procedures to be completed within 28 days of first dose, except labs. All labs should be collected within 14 days of first dose.

- 1) History and physical examination
- 2) Measurement of height, weight and vital signs (including blood pressure, heart rate, respiratory rate, oxygen saturation, and temperature).
- 3) Performance status evaluation
- 4) CBC with differential, serum chemistry (Na, K, Cl, CO₂, BUN, creatinine, glucose, calcium), magnesium, phosphate, amylase, lipase, liver function tests (albumin, total protein, alkaline phosphatase, total bilirubin, ALT, AST), LDH, TSH (with reflex to free T3 and free T4)
- 5) Pregnancy test (serum or urine) for women of childbearing potential. Sexually active women of childbearing potential must use an effective method of birth control during the course of the study, in a manner such that risk of failure is minimized.
- 6) Systemic tumor assessment with CT scan of the chest/abdomen/pelvis and CT or MRI Brain (MRI preferable). MRI brain required only if known or suspected brain metastases.

If eligible, a tumor biopsy and blood draw for research studies (approximately 2 tablespoons of blood) will be performed prior to initiation of therapy (see section 4.1.1).

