- Lytic bone lesions or mixed lytic-blastic lesions, with identifiable soft tissue components, that can be evaluated by cross-sectional imaging techniques such as CT or MRI can be considered measurable lesions if the soft tissue component meets the definition of measurability described above.
- Blastic bone lesions are non-measurable.

Cystic lesions:

- Lesions that meet the criteria for radiographically defined simple cysts should not be considered malignant lesions (neither measurable nor non-measurable) since they are, by definition, simple cysts.
- Cystic lesions thought to represent cystic metastases can be considered measurable lesions if they meet the definition of measurability described above. However, if non-cystic lesions are present in the same patient, these are preferred for selection as target lesions.

Lesions with prior local treatment:

- Tumor lesions situated in a previously irradiated area, or in an area subjected to other loco-regional therapy, are usually not considered measurable unless there has been demonstrated progression in the lesion. For this study, such lesions will be considered measurable if they are clearly progressing and meet other RECIST 1.1 criteria.

Target Lesions: Specifications by Methods of Measurements**a. Measurement of Lesions**

All measurements should be recorded in metric notation, using calipers if clinically assessed. All baseline evaluations should be performed as close as possible to the treatment start and never more than 4 weeks before the beginning of the treatment.

b. Method of Assessment

The same method of assessment and the same technique should be used to characterize each identified and reported lesion at baseline and during study. Imaging-based evaluation should always be the preferred option.

Clinical Lesions. Clinical lesions will only be considered measurable when they are superficial and ≥ 10 mm in diameter as assessed using calipers (e.g., skin nodules). For the case of skin lesions, documentation by color photography, including a ruler to estimate the size of the lesion, is suggested.

Chest X-Ray. Chest CT is preferred over chest X-ray, particularly when progression is an important endpoint, since CT is more sensitive than X-ray, particularly in identifying new lesions. However, lesions on chest X-ray may be considered measurable if they are clearly defined and surrounded by aerated lung.

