A sum of the diameters (longest for non-nodal lesions, short axis for nodal lesions) for all target lesions will be calculated and reported as the baseline sum of diameters. If lymph nodes are to be included in the sum, then, as noted above, only the short axis is added into the sum. The baseline sum of diameters will be used as a reference to further characterize any objective tumor regression in the measurable dimension of the disease.

All other lesions (or sites of disease), including pathological lymph nodes, should be identified as non-target lesions and should also be recorded at baseline. Measurements are not required and these lesions should be followed as “present,” “absent,” or in rare cases “unequivocal progression.”

In addition, it is possible to record multiple non-target lesions involving the same organ as a single item on the Case Report Form (CRF) (e.g., “multiple enlarged pelvic lymph nodes” or “multiple liver metastases”).

Response Criteria

a. Evaluation of Target Lesions

This section provides the definitions of the criteria used to determine objective tumor response for target lesions.

- Complete response (CR): disappearance of all target lesions

Any pathological lymph nodes (whether target or non-target) must have reduction in short axis to < 10 mm.

- Partial response (PR): at least a 30% decrease in the sum of diameters of target lesions, taking as reference the baseline sum of diameters
- Progressive disease (PD): at least a 20% increase in the sum of diameters of target lesions, taking as reference the smallest sum on study (nadir), including baseline

In addition to the relative increase of 20%, the sum must also demonstrate an absolute increase of at least 5 mm.

The appearance of one or more new lesions is also considered progression.

- Stable disease (SD): neither sufficient shrinkage to qualify for PR nor sufficient increase to qualify for PD, taking as reference the smallest sum on study

b. Special Notes on the Assessment of Target Lesions

Lymph Nodes. Lymph nodes identified as target lesions should always have the actual short axis measurement recorded (measured in the same anatomical plane as the baseline examination), even if the nodes regress to < 10 mm on study. This means that when lymph nodes are included as target lesions, the sum of lesions may not be zero even if CR criteria are met since a normal lymph node is defined as having a short axis < 10 mm.

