Appendix 4: Immune-Related Response Criteria

INTRODUCTION

Increasing clinical experience indicates that traditional response criteria (e.g., Response Evaluation Criteria in Solid Tumors, Version 1.1 [RECIST v1.1] and World Health Organization [WHO]) may not be sufficient to characterize fully activity in the new era of target therapies and/or biologics. In studies with cytokines, cancer vaccines, and monoclonal antibodies, complete response, partial response, or stable disease has been shown to occur after an increase in tumor burden as characterized by progressive disease by traditional response criteria. Therefore, conventional response criteria may not adequately assess the activity of immunotherapeutic agents because progressive disease (by initial radiographic evaluation) does not necessarily reflect therapeutic failure. Long-term effect on the target disease must also be captured. The immune-related response criteria¹⁹ (irRC) are criteria that attempt to do that by enhancing characterization of new response patterns that have been observed with immunotherapeutic agents (i.e., ipilimumab). (Note: The irRC only index and measurable new lesions are taken into account.)

GLOSSARY

| Term | Definition |
|--------------|---|
| SPD | sum of the products of the two largest perpendicular diameters |
| Tumor burden | $SPD_{\text{index lesions}} + SPD_{\text{new, measurable lesions}}$ |
| Nadir | minimally recorded tumor burden |
| irCR | immune-related complete response |
| irPD | immune-related progressive disease |
| irPR | immune-related partial response |
| irSD | immune-related stable disease |
| irBOR | immune-related best overall response |

BASELINE ASSESSMENT USING irRC

Step 1. Identify the index lesions (five lesions per organ, up to ten visceral lesions and five cutaneous lesions).

Step 2. Calculate the SPD of all of these index lesions:

$$SPD = \sum_i (\text{Largest diameter of lesion } i) \times (\text{Second largest diameter of lesion } i).$$

POST-BASELINE ASSESSMENTS USING irRC

Step 1. Calculate the SPD of the index lesions.

Step 2. Identify new, measurable lesions ($\geq 5 \times 5$ mm; up to five new lesions per organ: five new cutaneous lesions and ten visceral lesions).

Step 3. Calculate the SPD of the new, measurable lesions.

Step 4. Calculate the tumor burden:

$$\text{Tumor burden} = \text{SPD}_{\text{index lesions}} + \text{SPD}_{\text{new, measurable lesions}}$$

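### One unconfirmed progression on prior anti-PD-1 therapy is enough for entry and may also serve as the RECIST baseline, so a late response to the prior drug, if it occurs, would count for the combination

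*Combined protocol and SAP*

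**What the plan says.** **Entry.** Criterion I in Section 3.1 requires that anti-PD-1 axis therapy "must be the most recent systemic anti-tumor treatment received in all patients, with documented progressive disease". For the primary cohort, I.a adds that patients "must have had progressive disease or stable disease less than 24 weeks as the best clinical response to anti-PD-1-axis monotherapy". Neither names the response criteria to be used, a second scan or a confirmation interval.

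**Timing.** The prior drug has a washout: "Last administration of anti-PD-1 axis therapy must have been at least 3 weeks before the first dose of study drug". Section 5.1 sets the screening window: "All procedures to be completed within 28 days of first dose, except labs". Appendix 3 agrees that baseline evaluations are "never more than 4 weeks before the beginning of the treatment". Only one rule ties the baseline scan to the end of a prior drug. It is in exclusion J of Section 3.2 and concerns another class: "The baseline scan must be obtained after discontinuation of prior TKIs".

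**Scoring.** A RECIST partial response is "at least a 30% decrease in the sum of diameters of target lesions, taking as reference the baseline sum of diameters". Section 8 requires on-trial responses to be confirmed at least 4 weeks later. Section 9 rejects the null at 4 or more responses in 40 patients, with a 5% null and a 19% alternative that it describes as examples without experimental basis.

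**The protocol's view of early progression.** Appendix 4 states that with immunotherapy "progressive disease (by initial radiographic evaluation) does not necessarily reflect therapeutic failure".

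**The concern.** Section 2.2 asks whether adding ipilimumab to nivolumab produces regression after primary resistance to PD-1 blockade. That requires that patients called resistant really are resistant. Appendix 4 warns that a first progression on immunotherapy may be followed by response, yet criterion I takes a first progression at face value for the drug that defines the population.

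Suppose a tumor enlarges and then shrinks under the earlier anti-PD-1 drug. The patient can enter with progression as best response, have baseline measured near the peak, restart PD-1 blockade as part of the trial regimen, and reach a 30% decrease. There is no control arm to show what PD-1 blockade alone would have done. Confirming the on-trial response verifies the shrinkage, not its cause. With a cut-off of 4, one such patient supplies a quarter of what is needed.

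**Working it through.** **1. Can one scan serve both purposes?** Count days back from first dose (day 0).
- Earliest permitted baseline CT: day −28 (Section 5.1, Appendix 3).
- Latest permitted prior anti-PD-1 dose: day −21 (criterion I).
- Any CT in the 28-day window that shows progression can be both the entry evidence and the baseline. No text forbids it.
- The baseline CT may even precede the last prior dose, by up to 28 − 21 = 7 days.

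This is permitted, not required. A patient with an earlier progression scan and a fresh screening CT does not have the problem in this form.

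**2. Reproduce the plan's figures.** Inputs from Section 9: first stage 10 patients, stop at no responses; total 40; reject at 4 or more. With true response probability p,

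P(reject) = Σ over x = 1 to 10 of Bin(x; 10, p) × P[Bin(30, p) ≥ 4 − x].

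At p = 0.05: 0.3151 × 0.1878 + 0.0746 × 0.4465 + 0.0105 × 0.7854 + 0.0010 = 0.102. At p = 0.19 the sum is 0.857. These match the stated significance level of 0.1 and power above 85%.

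The written first-stage rule also lets prolonged irRC stability carry the trial forward. That raises the 0.102 toward a ceiling of P[Bin(40, 0.05) ≥ 4] = 0.138. The figures below use the response-only rule, as the plan's own figures do.

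**3. Effect of late responders.** The documents give no share, so d = 2, 3 and 5% is an assumption. What d does depends on what the 5% null already contains.

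- *Reading A:* late responses to PD-1 blockade are the only background responses, so p = d.
- *Reading B:* they add to a separate 5%, so p = 0.05 + d.

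| Assumed d | Expected late responders in 40 | P(reject), A | P(reject), B |
|---|---|---|---|
| 2% | 0.8 | 0.006 | 0.231 (p = 0.07) |
| 3% | 1.2 | 0.023 | 0.306 (p = 0.08) |
| 5% | 2.0 | 0.102 | 0.454 (p = 0.10) |

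If reading B lets late responses arise only among patients who would not otherwise respond, p = 0.05 + 0.95d and the figures are 0.224, 0.294 and 0.436. The choice between A and B matters far more than this detail.

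**The case against.** **The null may already cover it.** If ipilimumab adds nothing, patients are simply receiving PD-1 blockade again, and late PD-1 responses are the natural content of a 5% background. Under reading A no assumed share up to 5% takes the rejection probability above the design's own 0.102. This stands. It does not settle the matter, because Section 9 says the 5% is an example without evidence behind it, so the documents do not show that it was meant to cover such responses.

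**There is no contradiction with on-trial rules.** A reader might infer that the protocol breaks its own rule by confirming progression on trial but not at entry. The documents do not support that. Confirmed progression belongs to irRC, a secondary measure. The primary endpoint is RECIST v1.1, whose on-trial progression generally needs no confirming scan. Treatment beyond progression in Section 4.6 is conditional and does not cancel a RECIST progression. What remains is Appendix 4's general caution.

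**The TKI rule has its own reason.** Approved TKIs may stop just over 7 days before dosing, so up to about 20 days of the scan window could be on drug, against at most 7 for anti-PD-1 therapy. The difference is explicable, and its absence for anti-PD-1 drugs is not in itself an error.

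**Scan timing can cut the other way.** In a truly progressing patient, an early baseline charges growth before treatment to the trial regimen and makes a 30% decrease harder to reach. This also stands. It means early baselines do not bias the ORR in one direction only. It does not change how a late response to the prior drug would be attributed.

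**Frequency.** Appendix 4 speaks of several kinds of immunotherapy and gives no rate for NSCLC. Patients who had stable disease before progressing fit the pattern less well.

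**Conclusion.** The gap is real but its size is unknown. Entry rests on one unconfirmed progression, that scan may be the baseline, and nothing in the plan separates a late response to the prior drug from a response to the combination.

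A reader might take 0.231 to 0.454 as the trial's actual false-positive risk. The documents do not support that. Those figures need both an assumed late-responder share and the further assumption that it lies on top of a separate 5%. If late responders are the whole background, the same shares give 0.006 to 0.102. Both ranges belong in any discussion of the result.

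The sample-size arithmetic is not in error. The point concerns what 4 of 40 can be said to show about added ipilimumab, and it merits a modest change to data collection and reporting.

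**What to change.** 1. **Flag and report.** Add one CRF field: is the baseline scan itself the first scan to show progression on prior anti-PD-1 axis therapy? Prespecify that the primary-cohort RECIST ORR, with exact confidence intervals, is reported with and without flagged patients beside the 4-of-40 result. The decision rule stays on all 40, since the cut-off of 4 was not set for a subset.
2. **Use the earlier scan where there is one.** If progression was first seen on a scan before the screening CT, compare the two. Do not count a patient already regressing as primary resistance. This cannot help when the baseline is itself the first progression scan, which is why item 1 is needed.
3. **State the null's meaning.** Say in Section 9 whether the 5% is meant to include late responses to prior PD-1 blockade, and show both ranges.
4. **Optional tidy-up.** Extend the baseline-scan wording of exclusion J to anti-PD-1 therapy. This does not confirm progression: a last dose on day −24 and a first-progression CT on day −22 would satisfy it with the problem intact. It may also need a repeat CT in the few patients dosed after the scan.

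**Cost.** Items 1 to 3 need one CRF field, some wording and no added scan. An occasional patient will not be enrolled in the primary cohort, and the sensitivity ORR will rest on a smaller group with wide intervals.

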3.2. Exclusion Criteria

- A. Has an active autoimmune disease requiring systemic treatment within the past 3 months or a documented history of clinically severe autoimmune disease, or a syndrome that requires systemic steroids or immunosuppressive agents. Subjects with vitiligo or resolved childhood asthma/atopy would be an exception to this rule. Subjects who require intermittent use of inhaled steroids or local steroid injections would not be excluded from the study. Subjects with hypothyroidism stable on hormone replacement, or psoriasis not requiring systemic therapy (within the past 3 years) will not be excluded from the study.
- B. Interstitial lung disease that is symptomatic or may interfere with the detection or management of suspected drug-related pulmonary toxicity
- C. Subjects must not have a history of life-threatening toxicity related to prior anti-PD-1 axis therapy
 - a. Subjects with history of anti-PD-1 axis therapy toxicities that are unlikely to recur with standard countermeasures (e.g., hormone replacement after adrenal crisis) are eligible.
- D. Prior treatment with anti-CTLA-4 therapeutic antibodies
- E. Symptomatic or untreated CNS metastases. Patients with a history of treated asymptomatic CNS metastases are eligible, provided they meet all of the following criteria:

- a. No evidence of interim progression between the completion of CNS-directed therapy and the start of trial therapy.
 - b. No ongoing requirement for dexamethasone as therapy for CNS disease; anticonvulsants at a stable dose are allowed.
 - c. Completed stereotactic radiosurgery at least 1 week prior to Cycle 1, Day 1 or whole-brain radiation at least 2 weeks prior to Cycle 1, Day 1
- F. History of leptomeningeal carcinomatosis
- G. Prior palliative radiotherapy outside the CNS within 2 weeks of the first dose of study drug.
- H. Treatment with systemic immunosuppressive medications (including but not limited to, dexamethasone at doses > 2 mg daily (or equivalent dose of other corticosteroids), cyclophosphamide, tacrolimus, sirolimus, azathioprine, methotrexate, thalidomide, and antitumor necrosis factor [anti-TNF] agents) within 2 weeks prior to initiating trial therapy (Inhaled or topically applied steroids, and acute and chronic standard-dose NSAIDs are permitted. Replacement steroids are also permitted).
- I. Subjects must not have received vaccines containing live virus for prevention of infectious diseases within 12 weeks prior to the first dose of study drug.
- a. The use of inactivated seasonal influenza vaccines (eg, Fluzone®) will be permitted on study without restriction.
- J. Any approved systemic anti-cancer therapy, within 3 weeks prior to initiation of study treatment; the following exception is allowed:
- TKIs approved for treatment of NSCLC discontinued > 7 days prior to Cycle 1, Day 1. The baseline scan must be obtained after discontinuation of prior TKIs.
- K. Treatment with any other investigational agent or participation in another clinical trial with therapeutic intent within 21 days prior to enrollment; the following exceptions are allowed:
- Unapproved/experimental TKIs discontinued 14 days prior to Cycle 1, Day 1
- L. Known infection with HIV, HBV or HCV. Patients with prior exposure to hepatitis, but no evidence of active or chronic infection, may be eligible.
- Subjects with positive hepatitis C antibody and negative quantitative hepatitis C by polymerase chain reaction are eligible.
- M. Active systemic infection requiring systemic antibiotic treatment within 72 hours prior to first dose of study treatment
- N. Uncontrolled intercurrent illness including, but not limited to, symptomatic congestive heart failure, unstable angina pectoris, or psychiatric illness/social situations that would limit compliance with study requirements
- O. Major surgery or traumatic injury within 4 weeks of starting study drug
- P. Women who are pregnant or lactating.

- Q. Any underlying medical condition that in the Principal Investigator's opinion will make the administration of study drug hazardous to the patient or would obscure the interpretation of adverse events.

